#### 11.1.3 Efficacy Analyses

# 11.1.4 Primary Efficacy Analyses

ESS mean absolute change from baseline to the end of the 6-week treatment period will be analysed with an ANCOVA model, with the baseline ESS as a covariate, region and treatment as a factor. Missing data in the 6-week ESS evaluation will be considered as a treatment failure, that is imputing the missing ESS reduction as 0. Least-squared (LS) absolute mean changes will be presented by treatment group together with their corresponding 95% confidence interval. Paired-comparisons will be performed without any multiplicity adjustment.

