#### 11.1.5 Secondary Efficacy Analyses

All secondary variables assessing a mean absolute or a mean relative change will follow a similar methodology as for the primary variable; i.e., mean changes of ESS (up to 2-week treatment period), SCOPA-Sleep (up to 2-week and 6-week treatment period), PDSS-2 (2-week and 6-week), MWT (6-week), polysomnography (6-week), UPDRS Part III (2-week and 6-week), motor function assessed by the wrist worn device (6-week), HAM-D (2-week, 6-week and follow-up), MoCA (6-week), and FSS (6-week).

The percentage of subjects who showed ESS clinical response (defined as an ESS decrease from baseline of at least 3.0 points and/or final ESS score ≤10) after 2 and 6 weeks of treatment will be described and compared between groups by means of a Chi-square test (or Fisher's exact test according to corresponding applicability). Percentages and difference between treatments will be expressed with their 95% confidence interval calculated with a binomial exact method.

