9.2.5 Polysomnography

Mean absolute change in the polysomnography parameters (as defined below) from baseline to the end of the 6-week treatment period:

Sleep Stage Parameters:

Total Recording Time (TRT) is defined as the time in minutes from “lights out” to “lights on”. Total Sleep Time (TST) is the total time in minutes asleep after sleep onset. To determine the how well the patient slept, the Sleep Efficiency (SE) is calculated by dividing the TST by the TRT and multiplying by 100. Sleep studies are recorded on 30 second “epochs”. Sleep onset is defined as the first epoch scored as any stage other than stage W. Sleep Latency (SL) is the time from “lights out” to the sleep onset. Latencies to sleep stages are determined from sleep onset to the first epoch of that sleep stage. Wake after Sleep Onset (WASO) is the time awake after sleep onset until “lights on”. To determine the percentage time spent in each of the sleep stages during the sleep study, the total minutes of the sleep stage is divided by the TST and multiplied by 100.

Sleep information:

Percentage of TST Ni (for i=1 to 3) is calculated as a percentage: $(\text{Minutes Ni} / \text{TST} * 100)$

Percentage of TST REM is calculated as a percentage: $(\text{Minutes REM} / \text{TST} * 100)$

Clinical Event Parameters:

Event (or arousal) index will be calculated as the number of events (arousal number) divided by TST and multiplied by 60 (events per hour).

Events Index= $(\text{Events}/\text{TST}) * 60$.

Arousal Index= $(\text{Arousal number}/\text{TST}) * 60$.

Index will be calculated for the events and arousal detailed below:

- Apnoea
- Hypopnea
- Apnoea + Hypopnea
- Limb Movement

Sponsor BenevolentAI Bio

Project Code ... BB-2001-201b

- Periodic Limb Movement
- Arousals index
- Spontaneous Arousals index
- Apnoea Arousals index
- Hypopnea Arousals index
- LM Arousals index
- PLM Arousals index
- Desaturation Arousals index
- Snore Arousals index
- Respiratory Arousals index
- Respiratory Effort Related Arousal (RERA) index
- User Defined Arousals index
- Total Arousals index

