10.2 Secondary Efficacy Analysis

All secondary endpoints evaluated through a mean absolute change will follow a similar statistical analysis as for the primary variable (ANCOVA, considering baseline corresponding endpoint evaluation as covariate and treatment and region as fixed factors):

- Mean changes of ESS (up to 2-week treatment period)
- Mean relative change in the Epworth Sleepiness Scale (ESS) from baseline to the end of the 2-week and 6-week treatment periods (percentage of absolute decrease compared to baseline ESS).
- SCOPA-Sleep (up to 2-week and 6-week treatment period)
- PDSS-2 (2-week and 6-week)
- MWT (6-week)
- Polysomnography (6-week)
 - o Sleep Efficiency
 - o Percentage of TST REM
- UPDRS Part III (2-week and 6-week)
- Motor function assessed by the wrist worn device (6-week)
- HAM-D (2-week, 6-week and follow-up)
- MoCA (6-week), and FSS (6-week).
- Fatigue Severity scale (FSS)
- Polysomnography (6-week): Baseline index will not be considered in these Logistic models.
 - o Events Index (Increase in Events Index)
 - o Arousal Index (Increase in Arousal Index)

Categorical variables as detailed below will be analysed through fitted logistic regression model adjusted on baseline corresponding endpoint evaluation as a covariate and treatment and region as fixed factors. This model will estimate the adjusted Odds Ratio between treatment arms, its corresponding 95% and P-value.

- ESS clinical response, defined as ESS absolute decrease from baseline of at least 3.0 points, after 2 and 6 weeks of treatment.
- ESS clinical response, defined as $ESS \leq 10$ after 2 and 6 weeks of treatment.
- ESS clinical response, defined as either $ESS \leq 10$ after 2 and 6 weeks of treatment or ESS absolute decrease from baseline of at least 3.0 points after 2 and 6 weeks of treatment.

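### SAP 10.2 analyses the polysomnography event and arousal indices as an undefined yes/no increase by logistic regression without baseline, where the protocol sets mean change by baseline-adjusted ANCOVA, and section 14 records no change

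*SAP*

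**What the plan says.** Protocol 6.2.2 makes polysomnography a secondary endpoint, measured as mean absolute change from baseline to week 6. Protocol 11.1.5 includes 6-week polysomnography, with no parameter excepted, under the rule "All secondary variables assessing a mean absolute or a mean relative change will follow a similar methodology as for the primary variable". Protocol 11.1.4 gives that method as ANCOVA "with the baseline ESS as a covariate, region and treatment as a factor".

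SAP 9.2.5 sets the endpoint as "Mean absolute change in the polysomnography parameters (as defined below) from baseline to the end of the 6-week treatment period". Among the parameters it then defines are event and arousal indices, expressed per hour of sleep: "Index will be calculated for the events and arousal detailed below".

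SAP 10.2 opens with the general model for change endpoints, "ANCOVA, considering baseline corresponding endpoint evaluation as covariate and treatment and region as fixed factors", and lists Sleep Efficiency and the REM percentage under it as ordinary items. At the end of the same list come the indices, with the outcome written as an increase (for example "Arousal Index (Increase in Arousal Index") and the instruction "Polysomnography (6-week): Baseline index will not be considered in these Logistic models". The next paragraph says that categorical variables use logistic models "adjusted on baseline corresponding endpoint evaluation as a covariate and treatment and region as fixed factors", and lists only the ESS responses.

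SAP section 1 states that the SAP leaves the protocol's analysis unaltered. Section 14 states that the statistical content has not changed.

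**The concern.** For these indices SAP 10.2 changes four things together: the outcome (change in events per hour becomes yes/no), the model (ANCOVA becomes logistic), the covariate (baseline is dropped) and the reported effect (a difference in events per hour becomes an odds ratio). This goes beyond choosing which polysomnography parameters to test. It also departs from the SAP's own rule that logistic models adjust for baseline.

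The SAP does not say how large a rise counts. Two programmers could produce different results, and under the plainest reading a rise of 0.1 per hour counts the same as a rise of 20. What is at stake is the planned dose-versus-placebo comparison of sleep fragmentation in a small subset. By-arm descriptive means may still be produced under SAP section 7.

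**Working it through.** **1. The texts side by side**

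| Place | Outcome for the indices | Model |
|---|---|---|
| Protocol 6.2.2 | mean absolute change (polysomnography as a whole) | none named |
| Protocol 11.1.5 with 11.1.4 | mean change | ANCOVA: baseline, region, treatment |
| SAP 9.2.5 | mean absolute change, indices included | none named |
| SAP 10.2, opening sentence | mean change | ANCOVA: own baseline, region, treatment |
| SAP 10.2, index entry | an increase | logistic, baseline left out |
| SAP 14 | no change recorded | no change recorded |

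The conflict is in current text and needs no assumption.

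**2. The plan's own figure.** The protocol Summary gives at least 20 per group for polysomnography and MWT, at an effect size of 1.0 stated for MWT change. No power is stated. At an assumed 80% and two-sided 0.05, a two-sample t-test needs 17 per group, and 17 / 0.85 = 20. Power with 20 per group is 0.87. The figure is reproduced.

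Now apply the same effect, one SD of the change score, to a binary increase (change above 0, normal scores, placebo mean change 0). The proportions are 50% and 84% (or 16%), and power at 20 per group falls to 0.64. For assumed placebo mean changes from -1 to +0.5 SD it lies between 0.32 and 0.69, and 80% power would need 26 to 69 per group. With baseline adjustment, the continuous analysis has power of about 0.97 / 0.95 / 0.92 at correlations 0.3 / 0.5 / 0.7.

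**3. Simulation of the two models.** Four arms of 20, three regions, one arm shifted by 0.8 SD of the index, two-sided 0.05, 3,000 runs per cell. ANCOVA regresses change on treatment, region and baseline. The logistic model regresses change above 0 on treatment and region. The documents give no correlation r, effect size or distribution, so all three are assumptions.

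| Power (%) | r = 0.3 | r = 0.5 | r = 0.7 |
|---|---|---|---|
| Normal index, ANCOVA | 72 | 81 | 93 |
| Normal index, logistic without baseline | 36 | 47 | 61 |
| Log-normal index, Blom-rank ANCOVA | 69 | 76 | 87 |
| Log-normal index, logistic without baseline | 36 | 46 | 61 |

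Type I error was 0.044 to 0.058 for every method.

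**4. Analytic check for small effects.** With index SD 1, the variance per subject is 1 − r² under ANCOVA. For the sign of the change it is π(1 − r). The relative efficiency is (1 − r²) / [π(1 − r)] = (1 + r)/π = 0.41 / 0.48 / 0.54. So 20 per arm does the work of 8.3 / 9.5 / 10.8 per arm under ANCOVA.

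**5. Which part costs most.** A repeat of the normal case gave 35 / 46 / 60% for the logistic model without baseline, 44 / 52 / 64% with baseline added, and 72 / 81 / 93% for ANCOVA. Adding baseline recovers 9 / 6 / 4 points of a gap of 37 / 35 / 33. The rest, 28 / 29 / 29 points, comes from dichotomising.

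**6. Larger subset.** The footnote on MWT and polysomnography in protocol 18.15 says at least half of subjects. Half of 200 to 230 over four arms is 25 to 29 per arm. Logistic power is then 48 / 57 / 75% at 25 and 50 / 62 / 82% at 29. Both rows lie below ANCOVA at 20.

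**7. Chance baseline imbalance.** One standard error is sqrt(2/20) = 0.32 SD. With no drug effect it moves the proportion with an increase from 50% to 43 / 44 / 45%, an odds ratio of 0.74 / 0.78 / 0.82 and a log odds ratio of −0.30 / −0.25 / −0.20. The standard error of a log odds ratio at 20 per arm and 50% is sqrt(0.4) = 0.63, so the shift is 0.48 / 0.39 / 0.31 standard errors.

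**The case against.** The protocol asks for a similar method, not an identical one. It names polysomnography without naming any index and leaves full details to the SAP. That allows room for detail. It does not cover an unrecorded change of outcome, model, covariate and effect measure.

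The index entry stands last in its list, directly above the logistic paragraph, and may simply belong below it. If so, the clash with the opening sentence of SAP 10.2 is a matter of layout. The departures from protocol 11.1.5 and from the mean-change endpoint in SAP 9.2.5 remain, as does the explicit exclusion of baseline.

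Three stronger readings are tempting, and the documents support none of them:

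- A reader might infer that SAP 9.2.5 itself prescribes ANCOVA. It names no model; it fixes only the mean-change endpoint.
- A reader might infer that omitting baseline biases the test. Type I error is intact, and a one-standard-error imbalance moves the estimate by less than half its standard error. Baseline also presumably enters through the definition of an increase.
- A reader might infer that a sleep-safety signal would be missed. Insomnia is an adverse event of special interest, and Sleep Efficiency, PDSS-2 and SCOPA-Sleep are analysed by ANCOVA. The insomnia rates quoted in protocol 7.2 are for 10 mg/d; this trial stops at 3 mg/d, where rates are said to be lower without figures.

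It is also fair that 20 per arm is a planned minimum, so the power figures there are a floor, and that they read an increase as any increase.

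**Conclusion.** The departure is real and unrecorded: a mean-change endpoint with a baseline-adjusted ANCOVA has become an undefined binary outcome without baseline. If any rise counts, power for a 0.8 SD shift drops by 36 / 34 / 32 points at 20 per arm (72 − 36, 81 − 47, 93 − 61), mainly through dichotomising, and 29 per arm does not close the gap. These sizes rest on the assumed correlations, effect and distributions and on the any-rise reading; the textual conflict does not.

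The consequence is limited to secondary indices in a subset, among secondary analyses without multiplicity adjustment. The planned test is valid but inefficient, baseline imbalance is a minor matter, and no primary conclusion is affected. The change is optional but worthwhile, because it is cheap.

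**What to change.** In SAP 10.2, replace the index entry with:

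*Polysomnography Events Index and Arousal Index (6-week): change from baseline in events per hour, ANCOVA with baseline index, region and treatment; Blom-rank ANCOVA reported as a fixed sensitivity analysis regardless of residuals; proportion with any increase shown descriptively.*

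The rank analysis should be fixed in advance. Making it depend on how skewed the residuals look would add an undefined, data-dependent choice of method.

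If the sponsor prefers the logistic model, define the threshold for an increase, add the baseline index as a covariate, align the endpoint wording in 9.2.5 and record the departure in section 14.

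The cost is one SAP entry and one model swap on data the trial already collects, and the primary analysis of these indices keeps the same dose-versus-placebo contrasts. The downside is that the indices may be skewed, which the rank sensitivity analysis covers.

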14 CHANGES FROM THE PROTOCOL

There are no changes to the statistical content specified in the protocol.

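### The ESS responder endpoints have a Chi-square/Fisher test with a risk difference in the protocol but a logistic odds ratio in the SAP, and the SAP declares no change

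*SAP*

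**What the plan says.** Protocol 11.1.5, and the synopsis in the same sense, takes ESS response ("defined as an ESS decrease from baseline of at least 3.0 points and/or final ESS score ≤10") at 2 and 6 weeks. It says the percentages will be "described and compared between groups by means of a Chi-square test (or Fisher's exact test according to corresponding applicability"). It then fixes the effect measure: "Percentages and difference between treatments will be expressed with their 95% confidence interval calculated with a binomial exact method".

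SAP 10.2 lists three ESS response definitions: a decrease of at least 3.0 points, a score of 10 or less, and either of these. They match the three in protocol 6.2.2. For all three the SAP says: "Categorical variables as detailed below will be analysed through fitted logistic regression model adjusted on baseline corresponding endpoint evaluation as a covariate", with treatment and region as fixed factors. The output is stated as: "This model will estimate the adjusted Odds Ratio between treatment arms, its corresponding 95% and P-value". I read the incomplete phrase as a 95% confidence interval.

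SAP 1 says that the SAP leaves the protocol's analysis unchanged and that deviations belong in its section 14. SAP 14 reads: "There are no changes to the statistical content specified in the protocol".

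**The concern.** The test, the adjustment and the effect measure all differ between the two documents, and the section meant to record such differences says there are none. Both analyses can claim to be pre-specified. After unblinding, the report could present whichever p-value, or whichever scale of effect, looks better, and a reader could not tell from the documents which was meant to lead.

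The scale matters as well as the test. An odds ratio and a difference in percentages do not convert into one another without the placebo rate, and it is the difference with its interval that the SAP leaves out. A lesser point is that the SAP never names the baseline covariate for the responder models, although SAP 1 says the SAP should be exact enough to guide programming.

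**Working it through.** **Side by side**

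| | Protocol 11.1.5 | SAP 10.2 |
|---|---|---|
| Test | Chi-square or Fisher's exact | Logistic regression |
| Adjustment | None | Baseline covariate, region |
| Effect measure | Difference in percentages | Adjusted odds ratio |
| Interval | Exact binomial 95% | 95% for the odds ratio |
| Declared as a change | – | No (SAP 1, SAP 14) |

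Neither document gives a responder rate, power or sample size for these endpoints, so there is no planned figure to reproduce.

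**What the covariate means.** The same phrase appears earlier in SAP 10.2 for the continuous endpoints: "ANCOVA, considering baseline corresponding endpoint evaluation as covariate and treatment and region as fixed factors". Those endpoints are changes from baseline, so there the phrase can only mean the baseline score of the scale. The primary model also uses baseline ESS. A design matrix of intercept, three treatment terms, two region terms and baseline ESS has rank 7 with 7 columns, so the logistic model is estimable on that reading.

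**Odds ratio against difference in percentages.** For placebo rate p0 and odds ratio OR, p1 = OR × p0/(1 − p0) ÷ [1 + OR × p0/(1 − p0)]. Take OR = 2.5:

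- p0 = 10%: odds 0.111 × 2.5 = 0.278, p1 = 21.7%, difference 11.7 points
- p0 = 20%: odds 0.250 × 2.5 = 0.625, p1 = 38.5%, difference 18.5 points
- p0 = 30%: odds 0.429 × 2.5 = 1.071, p1 = 51.7%, difference 21.7 points

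**Rates implied by the planning values.** Inputs are a difference of 3.0 and SD 5.0 (protocol 11.2, SAP 5). A normal change score and a mean placebo change m of 0, −1 or −2 are assumptions. For a decrease of at least 3 points, p0 = Φ((−3 − m)/5) and p1 = Φ((−3 − (m − 3))/5) = Φ(−m/5).

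| m | p0 | p1 | Difference | OR | Power, 50 per arm |
|---|---|---|---|---|---|
| 0 | 27.4% | 50.0% | 22.6 points | 2.65 | 64% |
| −1 | 34.5% | 57.9% | 23.5 points | 2.62 | 66% |
| −2 | 42.1% | 65.5% | 23.5 points | 2.62 | 66% |

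At such power many trials land near the 0.05 line, where two different tests can part.

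**How often they part.** Trials were simulated with 50 per arm, a true effect of 3 points and SD 4 to 5. The baseline distribution and placebo change were assumed (one set-up: baseline 13 to 24, placebo change −1 to −3), and region was omitted. Chi-square/Fisher was compared with logistic regression on treatment and baseline ESS. The verdicts at 0.05 differ in:

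- roughly 8% to 14% of trials for ESS of 10 or less
- about 1% to 3% for a decrease of at least 3 points

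Two variations of the first figure show what drives it. Letting baseline scores fall to 9 gave 14% to 16%. Replacing baseline ESS by a constant gave 0.3% to 3.7%. Most of the disagreement therefore comes from adjusting for baseline ESS, which largely determines who can reach 10.

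**The case against.** The SAP's model is arguably the better one. In the simulations, adjusting for baseline ESS added about 1 to 7 points of power for ESS of 10 or less. Protocol 11.1 leaves full details to the SAP. SAP 7 tabulates counts and percentages by arm, so a reader will see the rates behind any odds ratio. These are secondary endpoints in a phase 2b trial without multiplicity control, and the primary ESS analysis is untouched. All of that stands, and it limits the weight of the point. It does not make the no-change statement true, and tabulated percentages do not supply the promised interval for the difference. SAP 1 names Amendment 03 as its reference and the protocol compared here is Amendment 04, but the two current texts differ whatever their history.

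A reader might infer more: that the baseline covariate is constant for ESS of 10 or less, does not exist for the decrease definition, and so makes the model unusable. The documents do not support this.

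- It requires reading the phrase as baseline responder status. The parallel ANCOVA sentence points to the baseline score, which varies and can be estimated.
- Even on the literal reading, constancy does not follow. The ESS criterion of more than 12 is tied to screening, while the efficacy baseline is the last value before randomisation, taken at Day −1. The criteria are reconfirmed, but nothing says that the cut-off is applied again to that score. Assuming bivariate normal scores with mean 12 to 16, SD 3.5 to 5.0 and correlation 0.6 to 0.9, between 0.4% and 17% of eligible patients, about 1 to 35 of 200, would have a baseline of 10 or less.

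What remains of the covariate question is that the variable should be named.

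**Conclusion.** The discrepancy is real and follows from the text alone: two tests and two effect measures for the same endpoints, and a false statement that nothing changed. The disagreement rates depend on the assumed baseline and placebo values, on omitting region, and on reading the covariate as the baseline ESS score. They show that the choice can decide the reported result, mainly for ESS of 10 or less, and they are not predictions for this trial. Naming the covariate is a clarification and does not repair a broken model. Because only secondary endpoints are involved, this should be corrected before unblinding but does not threaten the trial's main conclusion.

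**What to change.** Before unblinding:

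1. In SAP 10.2, declare one main analysis for the responder endpoints. One option is the logistic model with treatment, region and continuous baseline ESS total score, named explicitly as the last value before randomisation. Keeping the protocol's test as the main analysis would also do, with the logistic model marked as an addition.
2. Report the difference in responder percentages between each dose and placebo, with a 95% confidence interval, next to the odds ratio.
3. In SAP 14, list the replacement of the Chi-square/Fisher test and correct the matching statement in SAP 1. The protocol specifies an exact binomial interval, not a model-standardised difference. If a standardised difference is used instead, list that as a further change.
4. Complete the sentence on the odds ratio so that it names the confidence interval.

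The cost is a few lines of SAP text and one extra estimate in existing programs. No data collection changes.

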10.3 Exploratory Efficacy Analysis

We aim to characterise the changes in free-living activity by means of wrist-worn actigraphy. GENEActiv accelerometers are worn on the wrist and measure tri-axial acceleration with a sample

frequency of 100Hz. The device also measures temperature and light levels. The data is collected pre- and post- dosing (V3), each over a period of seven days. We aim to measure differential physical activity behaviour, and also the length and frequency of daytime sleep episodes.

The data is to be processed using the calibrated GENEActiv tracker data pre-processing package in R. We extract 12-hour daytime records and convert the accelerometer to gravity-subtracted Signal Vector Magnitudes (SVMgs), which is our measure of instantaneous physical intensity. The time-series is downsampled (100x) to one second intervals by averaging the instantaneous SVMgs across the 100 time points. The averaged SVMgs are grouped into four intensity levels groups: Sedentary (< 4.5), Light (4.5-16.5), Moderate (16.5-42), and Vigorous (> 42). These threshold boundaries may change as thresholds used in existing studies are calibrated for different populations. The summary statistics we aim to extract are bout lengths and frequencies, where a bout is a continuous episode of physical activity at a specific intensity levels band. Using paired t-tests, we aim to demonstrate a reduction in sedentary activity and an increase in light to vigorous activity in the dosed population. Using automatic changepoint detection methods (such binary segmentation methods and its extensions, with the fused lasso total variation regulariser, together with Bayesian approaches such as Dirichlet process hidden Markov models.) for detection of sleep boundary times, we also, independently of activity level measurements, aim to quantify the frequency and lengths of daytime sleep episodes.

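### SAP 10.3 applies unitless cut-offs of 4.5/16.5/42 to a one-second mean of wrist acceleration; in g, essentially all time would be Sedentary

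*SAP*

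**What the plan says.** SAP 10.3 sets out a definite processing chain.

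- The device samples at a "frequency of 100Hz. The device also measures temperature and light levels".
- The software will "convert the accelerometer to gravity-subtracted Signal Vector Magnitudes (SVMgs), which is our measure of instantaneous physical intensity". No unit is given.
- The series is "downsampled (100x) to one second intervals by averaging the instantaneous SVMgs across the 100 time points".
- The cut-offs go on that average: "The averaged SVMgs are grouped into four intensity levels groups: Sedentary (< 4.5), Light (4.5-16.5), Moderate (16.5-42), and Vigorous (> 42"). They have no unit, source or calibration epoch.
- On the cut-offs it adds: "These threshold boundaries may change as thresholds used in existing studies are calibrated for different populations".
- Bout lengths and frequencies by band are the summaries, and they are to be tested: "Using paired t-tests, we aim to demonstrate a reduction in sedentary activity and an increase in light to vigorous activity in the dosed population".
- Daytime sleep episodes are derived separately. The SAP will, "independently of activity level measurements, aim to quantify the frequency and lengths of daytime sleep episodes".

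The protocol gives no cut-offs. SAP 9.3 lists free-living activity as an exploratory endpoint.

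**The concern.** Averaging 100 values leaves the result in the unit of one value, whereas summing them makes it 100 times larger. Cut-offs made for one are wrong by a factor of 100 for the other. Values of 4.5, 16.5 and 42 look far too large for a mean in g, and no other usual unit makes them sensible for a mean.

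SAP section 1 says the plan should be precise enough to guide programming. A programmer who followed 10.3 with data in g would code essentially every second as Sedentary. The bout summaries would then carry no information, and the planned test of less sedentary and more light-to-vigorous activity could not show an effect. Those data come from about half of the subjects, each asked to wear the device for 7 days twice (Protocol 8.4.1.15.9).

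**Working it through.** **1. The plan's own figure.** 100 Hz × 1 s = 100 samples, which reproduces the stated 100-fold downsampling. For any second, sum = 100 × mean. Cut-offs of 4.5/16.5/42 on a sum in g therefore equal 0.045/0.165/0.42 g (45/165/420 mg) on the mean.

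**2. The cut-offs on the mean, by unit** (1 g = 9.81 m/s2)

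| Unit of the averaged value | Light from | Moderate from | Vigorous above |
|---|---|---|---|
| g | 4.5 g | 16.5 g | 42 g |
| m/s2 (divide by 9.81) | 0.46 g | 1.68 g | 4.28 g |
| mg (divide by 1000) | 0.0045 g | 0.0165 g | 0.042 g |
| For comparison: 100-sample sum in g | 0.045 g | 0.165 g | 0.42 g |

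**3. What movement that implies.** Assume a sinusoidal hand movement along gravity, with amplitude A and frequency f, and take the absolute value of the gravity-subtracted signal. Peak acceleration is (2πf)²A and its mean absolute value is 2/π times that, so

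A = mean × (π/2) × 9.81 / (2πf)².

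- Mean 4.5 g at 1 Hz: 4.5 × 1.571 × 9.81 / 39.48 = 1.76 m. This is a lower bound, because the gravity-subtracted magnitude never exceeds the acceleration itself.
- Mean 0.042 g at 1 Hz: 0.042 × 1.571 × 9.81 / 39.48 = 0.016 m, or 1.6 cm.
- Mean 0.042 g at 5 Hz: 0.647 / 987 = 0.00066 m, or about 0.7 mm. The diagnostic criteria in Protocol Appendix 18.2 include rest tremor at 4-6 Hz, so on the mg reading a tremor of that size along gravity would be Vigorous.

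Worked case, 1 Hz and 10 cm: peak = 39.48 × 0.10 = 3.95 m/s2 = 0.402 g; mean = 0.402 × 2/π = 0.256 g. That is Sedentary in g (0.256), Sedentary in m/s2 (2.51), Vigorous in mg (256) and Moderate as a 100-sample sum in g (25.6).

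**4. Share of seconds in each band.** The documents give no distribution of wrist acceleration. Assumption: one-second means are lognormal, with median 0.01 to 0.08 g and log-SD 0.8 to 1.2. The share below a cut-off c is Φ(ln(c/median)/log-SD).

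| Reading | Share over the assumed range |
|---|---|
| Mean in g | Sedentary at least 99.96% |
| Mean in m/s2 | Sedentary about 93% to 100% |
| Mean in mg | Vigorous 4% to 79% (18% to 39% at medians of 0.02 to 0.03 g) |
| Sum in g | Sedentary 24% to 97%, Light 3% to 58%, Moderate 0% to 19%, Vigorous 0% to 8% |

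Extreme cases, both at median 0.08 g and log-SD 1.2: in g, Φ(ln(4.5/0.08)/1.2) = Φ(3.36) = 99.96%; in m/s2, Φ(ln(0.459/0.08)/1.2) = Φ(1.46) = 93%.

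On the mg reading, every second that the sum reading calls Light or higher (at least 45 mg) becomes Vigorous. On the m/s2 reading, everything that the sum reading calls Light or Moderate (below 0.42 g) becomes Sedentary.

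**The case against.** The strongest reply is that this is missing detail in an exploratory analysis. The SAP states no unit, the output scale of the pre-processing package cannot be seen from the documents, and the cut-offs are openly provisional. A collapse to one band would be obvious on the first run.

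Part of that stands. The intended scale cannot be confirmed, and typical wrist acceleration has to be assumed. The case for a sum in g is an inference from physical plausibility.

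It does not remove the point. The SAP says explicitly that the averaged values are banded, and no usual unit makes that rule workable. The sentence on changing boundaries concerns calibration in other populations. It does not address scale or aggregation, and it sets no criterion or deadline, so the cut-offs could be settled after the data are seen.

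A reader might infer more than the documents support:

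- **That the bands would otherwise be nearly all Vigorous.** In mg, low-movement seconds spread over the lower three bands, and Vigorous passes 70% only at the highest assumed median. The result also depends on taking absolute values, which the SAP does not state.
- **That the cut-offs can only be for a sum.** No unit or source is given, so this is not established.
- **That the free-living objective goes unanswered.** The sleep-episode analysis does not use the bands. Nor do the descriptive accelerometry statistics in Protocol 6.2.3 and 8.4.6.
- **That a secondary endpoint is affected.** SAP 10.2 lists "Motor function assessed by the wrist worn device (6-week") without defining it, and nothing ties it to these cut-offs.

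**Conclusion.** The point holds in limited form. As written, the banding rule does not work. In g, essentially every second is Sedentary and the planned paired t-tests on the bands cannot show change. In m/s2 nearly all time is Sedentary, and in mg slight movement counts as Vigorous. The factor of 100 between sum and mean is exact. The shares of time rest on the assumed lognormal range, and the amplitudes on sinusoidal movement along gravity with absolute values taken. A 100-sample sum in g is a plausible origin for the cut-offs but is not confirmed.

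The damage is confined to the exploratory activity-band analysis. The change is worth making because it is cheap and restores a planned test.

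**What to change.** In SAP 10.3:

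1. Check and cite the source of the cut-offs, with its unit, sampling rate, epoch and aggregation.
2. Make the aggregation match that source. If the cut-offs are for 100-sample sums in g, either sum the samples in each second and keep 4.5/16.5/42, or keep the mean and use 0.045/0.165/0.42 g. If the source used another scale, convert from that scale instead.
3. State the unit and epoch of the banded value, and whether absolute values are taken after gravity subtraction.
4. Fix the cut-offs before unblinding. If recalibration for this population is wanted, state the rule for it in advance.

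Cost: a few lines of SAP wording and about one line of processing code. No new data are needed.
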